16.1.2 MISSING DATA METHODS FOR PRIMARY EFFICACY VARIABLE

The primary analysis method for evaluating the primary efficacy endpoint is the likelihood-based analysis of repeated measures, a mixed model with repeated measures (MMRM) under an assumption that the missing observations of change from baseline WOMAC pain score are missing at random. To assess the robustness of the MAR assumption, sensitivity analyses which utilize multiple imputations and different assumption about unobserved outcomes will be performed, as detailed in [Section 16.1.4](#).

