16.1.4 COMPOSITE STRATEGY ANALYSIS FOR PRIMARY EFFICACY

Composite strategy will be applied to the stratum of subjects experiencing intercurrent events.

For the intercurrent events of study treatment discontinuation due to reasons related to study treatment (AE, LOE, etc.), the obtained WOMAC pain score will be addressed in the analysis by expecting the long-term benefit from the treatment for that subject to be zero from the time of intercurrent event. For the other intercurrent events, rescue medication use within 24 hours of WOMAC assessment, removal/detachment of study patch for more than 24 hours before WOMAC assessment, the obtained WOMAC pain score will not be included in the analysis.

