16.1.5 SENSITIVITY ANALYSIS OF PRIMARY EFFICACY VARIABLE

Further details of sensitivity analyses are provided in [Appendix 3](#).

Sensitivity analyses will be performed to assess the impact of assumptions about missing data patterns on the primary and key secondary efficacy inferences. Additional analysis due to intercurrent events occurring in the trial will be performed.

The intercurrent events are defined as:

1. Discontinuation due to reasons related to study treatment (e.g. AE, LOE, lack of compliance, deviation from protocol, etc.),
2. Rescue medication drug use within 24 hours of WOMAC pain assessment,

Noven Pharmaceuticals, Inc.

Protocol HP-5000-US-07

3. Removal/detachment of the patch for more than 24 hours before WOMAC pain assessment.

Table B provides details on how these intercurrent events will be used for the sensitivity analyses.

Table B: Sensitivity Analysis Methods for Intercurrent Events

Analysis	Endpoint	Methods for Intercurrent Events		
		Discontinuation related to Study Medication	Rescue Medication	Patch Removal/ Detachment
Primary Efficacy	Mean change in WOMAC pain score from baseline to Week 12	1. Pattern Mixture Model	1. Pattern Mixture Model	1. Pattern Mixture Model
		2. Copy Reference Model	2. Copy Reference Model	2. Copy Reference Model

Pattern-Mixture Model and Copy Reference Sensitivity Analyses of MMRM Approach:

Robustness of the primary results under MNAR (Missing not at random) mechanisms will be assessed using pattern-mixture model and copy reference imputation approaches. All sensitivity analyses will be based on the pattern mixture model using multiple imputation for the dropout reasons and their assumed pattern of missing data as follows:

- LOE as MNAR with other missing data as MAR
- LOE and AE as MNAR with other missing data as MAR
- Any reason (all dropout) as MNAR

a. Multiple Imputation: Pattern Mixture Model (PMM)

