The missing data due to early discontinuation will be imputed assuming MNAR following the approach described in Permutt (2016)¹. That approach will be implemented by imputing missing data first under the MAR assumption in each treatment group using multiple imputation and then adding a pre-defined $\Delta 1$ to each imputed value in the placebo group and adding a different pre-defined $\Delta 2$ to each imputed value in the active treatment group, then varying $\Delta 1$ and $\Delta 2$ over an enclosure of a plausible range of values. As noted in the article by Permutt (2016)¹, this is considered the most appropriate kind of sensitivity analysis for the missing data problem. Also, this imputation approach was documented on Page 89 of the NRC report (2010)².

Noven Pharmaceuticals, Inc.

Protocol HP-5000-US-07

b. Multiple Imputation: Copy Reference (Placebo) Approach

This is placebo-based imputation for missing data which will be implemented assuming missing data from the placebo group as MAR and also as MNAR. This will be performed by first implementing placebo-based imputation for missing data in the active treatment group and the placebo group (as MAR). Then, an adjustment for MNAR in both treatment groups will be implemented by adding a common shift (Δ) to the imputed data, worsening the imputed data further, in both the placebo and the active treatment groups as described in Koch and Wienner (2016)³. This step is necessary because it is possible to have a lower treatment discontinuation rate in the active treatment group than in the placebo group and it is important to consider a MNAR approach in the placebo group in such a case. Using a similar argument as in the previous paragraph, the shift Δ will assume similar values to those of $\Delta 1$ (while the case of $\Delta=0$ represents the common copy placebo method, where missing data from placebo are considered as MAR).

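### SAP 16.1.5 and Appendix 3 conflict on whether WOMAC scores deleted for rescue use or patch removal receive the MNAR shift

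*SAP*

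**What the plan says.** SAP 16.1.4 covers two events that do not require leaving the study: rescue use within 24 hours of the WOMAC assessment, and the patch being off for more than 24 hours before it. In both cases "the obtained WOMAC pain score will not be included in the analysis". The primary MMRM then runs "under an assumption that the missing observations of change from baseline WOMAC pain score are missing at random" (SAP 16.1.2).

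SAP 16.1.5 says that "Table B provides details on how these intercurrent events will be used for the sensitivity analyses". The table has a column each for discontinuation, rescue medication and patch removal or detachment, and enters the pattern-mixture and copy-reference models in all three. The text that follows says robustness under MNAR mechanisms "will be assessed using pattern-mixture model and copy reference imputation approaches".

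The next sentence bases all the sensitivity analyses on a pattern-mixture model "using multiple imputation for the dropout reasons and their assumed pattern of missing data as follows". Three patterns follow:

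- "LOE as MNAR with other missing data as MAR"
- "LOE and AE as MNAR with other missing data as MAR"
- dropout for any reason as MNAR, with no statement about other missing data.

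None of them names rescue or patch removal. The pattern-mixture paragraph adds: "The missing data due to early discontinuation will be imputed assuming MNAR following the approach". The copy-reference paragraph has no such limit in its imputation steps.

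Appendix 3 gives the implementation. Its steps impute missing data without restriction and add the shift to every imputed value. Its justification of the shift range speaks of subjects who discontinued, and its results are to be reported by dropout reason, with no index for rescue or patch removal.

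**The concern.** The same score is treated differently depending on which part of the plan is followed. Table B promises that scores removed for rescue or patch removal will enter the MNAR assessment. The list that defines the assessment has no place for them unless the subject also drops out. Two programmers could each follow the text faithfully and produce different sensitivity tables.

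This matters because MAR is hard to defend for some of these deletions. Amended protocol 9.11 describes target-knee rescue as taken because the study drug gives too little relief. Dropout for lack of efficacy has its own MNAR pattern; a score removed because of rescue taken for the same reason has none. If the list governs, the result is stress-tested for one of the three intercurrent events in Table B and not for the other two. If the choice of reading is made after unblinding, the robustness statement becomes post hoc.

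**Working it through.** **Tracing one score.** Take a subject who uses rescue the evening before Visit 8, attends the visit and stays in the study. The Week 12 score is obtained and then deleted under 16.1.4. The plan gives these answers for that score:

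| Text | Treatment of the score |
|---|---|
| 16.1.5, Table B | In both models |
| 16.1.5, patterns 1 and 2 | Other missing data, so explicitly MAR |
| 16.1.5, pattern 3 | Not a dropout, so outside it by implication |
| 16.1.5, pattern-mixture paragraph | Not missing through early discontinuation |
| 16.1.5, copy-reference paragraph | No restriction to dropout in the imputation steps |
| Appendix 3, steps | Imputed, so shifted |
| Appendix 3, justification and output | MNAR linked to discontinued subjects; rows by dropout reason |

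The Appendix 3 steps cannot be taken literally alongside the list. If every imputed value were shifted in every pattern, the three patterns would give the same result and reporting by dropout reason would have no purpose.

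**Checking the plan's own figure.** Appendix 3 uses four values of Δ1 (0, 1.3333, 2.6667, 4 for WOMAC pain) and six values of k2 (0, 0.2, 0.4, 0.6, 0.8, 1). 4 × 6 = 24, which matches its stated number of shift combinations.

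**What turns on the choice.** For the pattern-mixture analysis, giving deleted Week 12 scores the shift instead of leaving them MAR moves the treatment difference by

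movement = p_HP × (Δ1 + k2 × |LSMD|) − p_PBO × Δ1,

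where p is the share of Week 12 scores deleted in each arm. Higher WOMAC is worse, so a positive movement is against HP-5000. Δ1 and k2 are from Appendix 3. Assumed, because the documents do not give them: |LSMD| = 1 point, and p of 5% or 10% per arm. The absolute value is used because Appendix 3 says the shift worsens scores.

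- 5% / 5% (HP-5000 / placebo): maximum 0.05 × 5 − 0.05 × 4 = 0.05. Range 0 to 0.05.
- 10% / 10%: maximum 0.10 × 5 − 0.10 × 4 = 0.10. Range 0 to 0.10.
- 10% / 5%: maximum 0.10 × 5 − 0.05 × 4 = 0.30. Range 0 to 0.30.
- 5% / 10%: minimum (Δ1 = 4, k2 = 0) 0.05 × 4 − 0.10 × 4 = −0.20; maximum (Δ1 = 0, k2 = 1) 0.05 × 1 = 0.05. Range −0.20 to 0.05.

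If the list is followed, the movement from these scores is 0 for subjects who stay in the study.

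**Scale.** A trial with exactly 80% power at two-sided 0.05 has an expected z of 1.96 + 0.84 = 2.80. The dilution that brings this to 1.96 is 1 − 1.96/2.80 = 0.30, with the standard error unchanged. The worst corner of the 10% / 5% case reaches that only if 1 point is also the difference the trial was powered for, which cannot be checked.

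The copy-reference movement was not computed. It depends on the placebo distribution and on the correlation with earlier visits.

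**The case against.** A reader might infer that the SAP leaves these scores MAR in every sensitivity analysis and allows MNAR imputation only for early discontinuation. The documents do not support that. The Appendix 3 steps, to which 16.1.5 refers, reach every imputed value. The copy-reference paragraph is not tied to early discontinuation. The third pattern carries no clause making other missing data MAR. Table B itself names methods, not MNAR; the link comes from the text after it. A deleted score in a subject who later drops out might also be shifted, since the SAP does not say whether patterns attach to subjects or to values. What remains is a conflict, firm for subjects who stay in the study.

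A reader might also infer that the result will look more robust than it is. That does not follow. SAP 16.1.6 plans an MMRM with no adjustment for intercurrent events, which puts the obtained scores back and shows what deleting them did. It is not an MNAR test, because those scores may themselves be improved by rescue, but these deletions do not go wholly unexamined. The direction is also open: if the drug works, rescue should be commoner on placebo, and the 5% / 10% case runs mostly in favour of HP-5000.

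Deletions for rescue may be few. Protocol 9.11 bars rescue from Baseline to Visit 4, in the 2 calendar days before Visits 5 to 8 and on visit days, so rescue within 24 hours of those assessments would be a deviation. It also allows rescue for headache and fever, so not every such deletion reflects knee pain. That limits the likely size but does not settle the rule. It also bears on rescue only: amended protocol 8.2.3 encourages subjects who stop treatment to keep attending without it, and their scores can fall under the patch-off rule.

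**Conclusion.** The conflict stands. SAP 16.1.5 and Appendix 3 do not settle whether scores deleted under 16.1.4 receive the MNAR shift. For subjects who stay in the study, the pattern list makes them MAR explicitly in two patterns and by implication leaves them out of the third. If the list governs, no MNAR analysis covers two of the three intercurrent events that Table B assigns to it.

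The primary estimate is unaffected; what is undefined is its robustness test. The size cannot be determined from the documents. The range of 0.20 points in favour of HP-5000 to 0.30 against rests on the assumed 5% to 10% deletion and 1-point difference, and the upper end requires twice as many deletions on HP-5000 as on placebo. With equal rates the movement is at most 0.05 to 0.10 points. This should be corrected, but it does not by itself put the primary analysis in doubt.

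**What to change.** Before unblinding:

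1. Add a pattern to the 16.1.5 list, for both methods: scores removed for rescue or for patch removal or detachment, plus study-treatment-related discontinuation, as MNAR; all other missing data as MAR.
2. State that the dropout-only patterns leave the removed scores as MAR, and whether a removed score in a subject who later drops out follows the score or the subject.
3. Amend Appendix 3 so that, in each pattern, the shift and the placebo-based imputation apply only to the values designated MNAR, and add the matching row set to the output.
4. Reconcile the SAP list with amended protocol 13.4.3.1, which has two groups (study-treatment-related reasons as MNAR; unrelated or uncertain reasons as MAR). SAP 3.3 records no change from the protocol, although the lists differ. The new pattern uses the protocol's category, so define it by the reasons in protocol 8.2.3.

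Narrowing Table B to discontinuation and aligning Appendix 3 would also remove the conflict, but would leave these deletions without an MNAR test.

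The cost is SAP wording and one more row set in an existing sensitivity table. No new data are needed and the primary analysis does not change.

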This is placebo-based imputation for missing data which will be implemented assuming missing data from the placebo group as MAR and also as MNAR. This will be performed by first implementing placebo-based imputation (copying the distribution of WOMAC scores in the placebo group) for missing data in the active treatment group and the placebo group (as MAR). Then, an adjustment for MNAR in both treatment groups will be implemented by adding a common shift ( $\Delta$ ) to the imputed data, worsening the imputed data further, in both the placebo and the active treatment groups as described in Koch and Wiener (2016). This step is necessary because it is possible to have a lower treatment discontinuation rate in the active treatment group than in the placebo group and it is important to consider a MNAR approach in the placebo group in such a case. Using a similar argument as in the previous paragraph, the shift  $\Delta$  will assume similar values to those of  $\Delta 1$ , that is  $\Delta=1,2,4,8,12$  (while the case of  $\Delta=0$  represents the common copy placebo method, where missing data from placebo are considered as MAR).

Sensitivity analysis using different methods of handling missing data will provide useful information about effectiveness of the study drug and confidence in the reliability of the conclusions drawn. Programming details including SAS code will be provided in the SAP.

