3. STUDY DESIGN

3.1 GENERAL DESCRIPTION

This is a multicenter, randomized, double-blind, placebo-controlled Phase 3 study in the US

Noven Pharmaceuticals, Inc.

Protocol HP-5000-US-07

Statistical Analysis Plan

Page 14 of 58

evaluating the efficacy and safety of HP-5000 in subjects with OA pain of the knee.

The study will consist of up to a 28-day Screening Phase that will include a Washout Period of current prescription and over the counter (OTC) analgesics; a 12-week Double-blind Treatment Phase, and a 1-week safety Follow-up Phase.

Screening Phase: Subjects will be seen in the clinic where the study will be described to them and will be asked to sign the informed consent form (ICF). No screening procedures may begin prior to obtaining informed consent. After obtaining a written informed consent, subjects will be screened for participation in the study. The target knee for the purpose of the study will be defined as the one which causes the subject more pain than the other knee and will be identified at the Screening visit using the NRS score. During the Screening Phase, subjects will complete a daily electronic diary (eDiary) to record pain severity of their target knee. Subjects who satisfy the entry criteria will be instructed to begin the Washout Period for 7 to 14 days, or at least 5 half-lives, whichever is longer, prior to the Baseline Visit (Day 0).

During the Washout Period, current prescription and OTC analgesics will be discontinued. However, rescue medication (acetaminophen [APAP]) for the treatment of any other aches the subject might experience during the trial, such as headache, reduction of fever, and the target knee pain of OA (not for the non-target knee) will be permitted (a maximum of 2 g/day) except within 3 calendar days prior to the Baseline Visit (i.e., rescue medication is prohibited for 2 days until clinic visit on Day 0 and on the day of Baseline Visit [V3]). During the Washout Period, subjects will complete a daily eDiary to record rescue medication usage in addition to pain severity of their target knee. Following completion of the Washout Period, subjects will return to the clinic for their Baseline Visit (Day 0). Eligible subjects will be randomized to either HP-5000 or placebo in a 1:1 ratio.

Treatment Arm	Treatment
HP-5000	HP-5000 [REDACTED] patch Each patch contains [REDACTED] diclofenac sodium.
Placebo	HP-5000 [REDACTED] Placebo patch Each patch contains 0% [REDACTED] diclofenac sodium.

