Double-blind Treatment Phase: Subjects will apply a single patch to the target knee [REDACTED]

[REDACTED] After the removal of the patch [REDACTED], a new patch will be applied to a different site on the target knee. Subjects will be instructed to rotate the patch application site [REDACTED] to alternate sides (inner and outer) of the target knee. During the Double-blind Treatment Phase, subjects will also complete a daily eDiary to record patch application and removal time, adhesion, irritation, discomfort, and pain assessments; and

Noven Pharmaceuticals, Inc.

Protocol HP-5000-US-07

Statistical Analysis Plan

[figure not shown]
Page 15 of 58

amount of rescue medication (APAP) taken daily, if applicable. A maximum of 2 g/day of APAP will be allowed as rescue medication except from Baseline Visit until Visit 4, within 2 calendar days prior to all subsequent visits (V5, V6, V7, and V8), and on the day of the clinic visits (V4, V5, V6, V7, and V8).

NOTE: Subjects are NOT allowed to apply HP-5000 on the non-target knee at any time during the study.

Follow-up Phase: Subjects will have a safety visit approximately 7 days after the Week 12 End-of-Treatment Visit. The investigator or qualified study staff will contact all subjects by phone for continued safety monitoring of AEs. At the discretion of the investigator, subjects may have to return to the clinic for their Follow-up Visit.

Figure 1: A Schematic of the Study Design

Sample Size: Based on the HP-5000 Phase 2 study results, the assumed effect size of the test product in the pivotal study will be about [REDACTED]. The sample size of [REDACTED] subjects per treatment arm (or total of about [REDACTED] subjects) will be included in order to have 80% power to demonstrate statistically significant difference versus placebo using a 2-sided overall Type I Error rate of 0.05.

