Step 4: Step 0 through Step 3 are then repeated $m=100$ times and PROC MIANALYZE is then applied to combine the estimates using Rubin's combination rules.

Noven Pharmaceuticals, Inc.

Protocol HP-5000-US-07

Justification of the ranges of $\Delta 1$ and $\Delta 2$ values to cover the plausible domain of the missing values is supported by the following, using WOMAC Pain UB1. The $\Delta 1$ will assume a value ranging from 0 to 4. This UB1 of 4 for $\Delta 1$ is selected to be reasonably higher than 1 SD of the primary endpoint of the study and is used to cover wider range of imputations. For the case of the lower boundary of $\Delta 1=0$, the missing data in the placebo group are considered as MAR. For the case of upper boundary of the range of $\Delta 1=4$, the missing data in the placebo group are considered MNAR with a fixed worsening shift of 4 from the imputed values assuming MAR of all missing WOMAC data. Such a magnitude represents a reasonable upper bound for the range of deviation from MAR imputation. The boundaries of $\Delta 2$ are selected to start from $\Delta 2=\Delta 1$ to $\Delta 2=\Delta 1+LSMD$. With the starting values of $\Delta 2=\Delta 1$, MNAR data for discontinued subjects either from the active treatment group or the placebo group are worsened by the same shift from their imputed WOMAC total score based on MAR. With the upper boundary of $\Delta 2$ defined by $\Delta 2=\Delta 1+LSMD$, the MNAR data for discontinued subjects from the active treatment group will have their WOMAC imputed scores based on MAR worsened by larger amounts that are equal to the whole LSMD rather than a fraction of the LSMD (in addition to the $\Delta 1$).

b. Multiple Imputation: Copy Reference (Placebo) Approach

Step 0: Missing data in the placebo group are imputed using a multiple imputation technique assuming MAR.

Step 1: Missing data in the active treatment group are imputed based on the conditional distribution estimated from the placebo group using a multiple imputation technique.

Step 2: A range of common shifts ($\Delta=0, 1.3333, 2.6667, 4$ units – WOMAC Pain) are added to the imputed data in Step 0 for the placebo group and in Step 1 for the active treatment group to worsen imputed scores. ($\Delta=0, 4, 8, 12$ units – WOMAC Physical Functioning) ($\Delta=0, 0.6667, 1.3333, 2$ units – WOMAC Stiffness)

Step 3: The primary MMRM model is then applied to each of the complete datasets created from Step 0 through Step 2.

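### In the copy-reference analysis, a common worsening shift moves the estimate toward HP-5000 whenever HP-5000 has the smaller share of imputed scores, which is the case the plan cites

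*SAP*

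**What the plan says.** SAP 16.1.5 b and protocol 13.4.3.1 b describe the same two-stage method. Missing scores in both arms are first imputed from the placebo distribution. A single shift is then added to the imputed scores, described in the protocol as "worsening the imputed data further, in both the placebo and the active treatment groups". Both documents justify this second stage by noting that "it is possible to have a lower treatment discontinuation rate in the active treatment group than in the placebo group", so that data missing not at random should be considered for placebo too.

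Appendix 3 b Step 2 of the SAP implements it. For WOMAC pain, shifts of 0, 1.3333, 2.6667 and 4 "are added to the imputed data in Step 0 for the placebo group and in Step 1 for the active treatment group". The protocol lists shifts of 1, 2, 4, 8 and 12, with 0 as the ordinary copy-placebo analysis. Appendix 3 reports the LS mean difference, its 95% CI and a nominal p-value by dropout reason and shift.

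Arm-specific shifts appear only in the separate pattern-mixture analysis (SAP 16.1.5 a, Appendix 3 a). There the HP-5000 shift equals the placebo shift plus a fraction, from 0 to 1, of the LS mean difference in the primary analysis.

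**The concern.** A delta adjustment is meant to show how much worse the missing outcomes would have to be before the conclusion fails. Worsening both arms by the same amount penalises each arm in proportion to its imputed share. If placebo has more imputed scores, placebo pays the larger penalty and the contrast improves for HP-5000. The plan gives this very imbalance as its reason for the step.

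The interpretation of the sensitivity table is at stake. Rows labelled with progressively worse assumptions about missing data could show a progressively larger treatment benefit. They would carry no information on how poorly HP-5000 subjects with missing scores could have fared before the effect disappeared.

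**Working it through.** **The plan's own figures.** The SAP pain grid reproduces: (0, 1/3, 2/3, 1) x 4 = 0, 1.3333, 2.6667, 4. The sample size was set "in order to have 80% power to demonstrate statistically significant difference versus placebo", "using a 2-sided overall Type I Error rate of 0.05". The effect size and the number per arm are redacted, so that calculation cannot be repeated; this is not a fault in the plan.

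**Inputs.**
- From the documents: 1:1 allocation, two-sided 0.05, 80% power, the shift grid, and higher WOMAC scores meaning worse.
- Assumed: effect size 0.25 SD (range 0.20 to 0.30); SD 3.5 (Appendix 3 says that 4 is somewhat above 1 SD); 252 per arm, which gives 80% power at 0.25 (393 at 0.20, 175 at 0.30). The benefit d in observed scores is then 0.25 x 3.5 = 0.875.
- Assumed: pA and pP, the shares of Week 12 scores imputed and shifted on HP-5000 and placebo. The plan gives no rates.

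**Formulas.** Take copy-reference imputation as giving imputed HP-5000 scores no benefit on average:
- estimate = -d(1 - pA) + shift x (pA - pP)
- variance = sum over arms of (SD^2 + p(1 - p) x shift^2) / n

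The second term of the estimate is negative whenever pA < pP, whatever d, SD and n are.

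**Change due to the shift alone.** At shift 4: 4 x (0.10 - 0.20) = -0.4; 4 x (0.10 - 0.15) = -0.2; equal shares, 0.

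**Estimate (z) at each SAP shift, common shift in both arms:**

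| pA / pP | 0 | 1.3333 | 2.6667 | 4 |
|---|---|---|---|---|
| 10% / 20% | -0.788 (-2.53) | -0.921 (-2.93) | -1.054 (-3.26) | -1.188 (-3.53) |
| 15% / 20% | -0.744 (-2.39) | -0.810 (-2.57) | -0.877 (-2.70) | -0.944 (-2.78) |
| 19% / 20% | -0.709 (-2.27) | -0.722 (-2.29) | -0.735 (-2.26) | -0.749 (-2.19) |
| 20% / 20% | -0.700 (-2.24) | -0.700 (-2.22) | -0.700 (-2.15) | -0.700 (-2.04) |
| 20% / 10% | -0.700 (-2.24) | -0.567 (-1.80) | -0.433 (-1.34) | -0.300 (-0.89) |

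Worked cell, 10% / 20% at shift 4: estimate = -0.875 x 0.90 - 0.4 = -1.188; variance = (2 x 12.25 + 16 x (0.09 + 0.16)) / 252 = 0.1131; SE = 0.336; z = -3.53.

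**When z strengthens too.** At shift 4 with placebo at 20%, the gap in shares must exceed about 1.4 percentage points (effect size 0.20) to 2.1 (effect size 0.30).

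**Simulation check.** Placebo-based multiple imputation was simulated for 10% / 20%, with five visits, monotone dropout, Rubin's rules, 200 trials and 20 imputations, and an unadjusted Week 12 difference in place of the MMRM. Mean estimates were -0.82, -0.96, -1.09 and -1.23 across the four shifts. The proportions with p < 0.05 were 0.70, 0.82, 0.88 and 0.92.

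**Shifting HP-5000 only (10% / 20%).** Estimate = -0.788 + shift x 0.10; variance = (24.5 + 0.09 x shift^2) / 252. Results at the four shifts are -0.788 (-2.53), -0.654 (-2.09), -0.521 (-1.65) and -0.388 (-1.21, p about 0.23). In this example significance is lost between 1.3333 and 2.6667.

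**Does the pattern-mixture grid fill the gap?** Write L for the size of the LS mean difference, k for the fraction and D for the placebo shift. Imputation at random leaves imputed HP-5000 scores about L better than placebo's, so the estimate is -L + k x L x pA + D x (pA - pP). With pA < pP the least favourable cell is D = 0, k = 1, giving -L(1 - pA). For L = 0.875 and pA = 10% that is -0.788, the same as the zero-shift copy-reference cell. Even the largest HP-5000 shift only brings its imputed scores level, on average, with placebo's. If the LS mean difference is read with its sign (SAP 6.5 and 16.1.3), it is negative when the drug works, and the HP-5000 shift is then the smaller one; that sign needs clarifying.

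**The case against.** **The step does what it says.** It was introduced to allow placebo scores, as well as HP-5000 scores, to be missing not at random. That is fair, and the common-shift cells are legitimate as a description of that scenario. But they are listed as robustness checks on the primary result, and in the cited case they cannot weaken the point estimate.

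**The conservative cell is not hidden.** Shift 0 stays in the grid and is reported alongside the others. When HP-5000 has the lower share, it is the least favourable estimate in the set. This stands: the plan keeps one sound conservative check. The positive shifts add no further stress to the estimate.

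**Inference does not always strengthen.** A reader might infer that every larger shift yields a stronger p-value, or that equal shares make the step inert. Neither follows. At 19% against 20%, z weakens at shift 4 although the estimate improves. At 20% against 20%, z goes from -2.24 to -2.04 because the interval widens.

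**The ordering may not occur.** The relevant quantity is the share imputed and shifted at Week 12, not the discontinuation rate itself. Under the SAP patterns that treat only lack of efficacy, or lack of efficacy and adverse events, as not at random, the share should be counted for those reasons. Adverse-event dropout on HP-5000 could narrow or reverse the gap, and the shift would then be a genuine stress test.

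**Rescue and patch-off scores.** Because Table B of the SAP routes these through copy reference, a reader might infer that they widen the gap. The documents do not support that. Rescue is barred for 2 calendar days before Visits 5 to 8 and on visit days, so such deletions come from deviations, and nothing indicates that detachment is more frequent on placebo.

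**Conclusion.** The point holds for the point estimate, in the case the plan itself names. With a lower imputed share on HP-5000, each larger common shift favours HP-5000 by the shift times the gap in shares: 0.4 point at shift 4 for 10% against 20%, and 0.2 for 10% against 15%. The direction needs no assumption beyond that ordering. The sizes rest on assumed imputed shares, and the z-values also on the assumed SD, effect size and sample size.

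The protocol's 12-point shift would give 12 x 0.10 = 1.2 points for 10% against 20%. A reader might quote that as the size of the problem, but the SAP's pain grid stops at 4, so 0.4 is the relevant figure. Nor do the documents support reading this as a flaw in the primary analysis: the primary test and its type I error are untouched. What is missing is any cell, in either sensitivity grid, in which HP-5000 subjects with missing scores fare worse on average than placebo subjects with missing scores.

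**What to change.** In SAP Appendix 3 b Step 2 and protocol 13.4.3.1 b, before unblinding:

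- Add cells in which the shift is applied to the imputed HP-5000 scores only, with placebo shift 0, at each value the SAP lists for the endpoint.
- Report the shift at which significance is lost, if it is lost within the grid.
- Show the share of Week 12 scores imputed and shifted in each arm beside the results.
- Keep the common-shift cells, with a note that they do not stress the drug effect when HP-5000 has the lower imputed share.

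Do not require every HP-5000-only cell to be significant. A 4-point shift assumes that HP-5000 subjects with missing scores fare more than 1 SD worse than their placebo counterparts, and a working drug could fail that: p is about 0.23 in the 10% / 20% example. The loss-of-significance shift lets the reader judge plausibility.

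The cost is wording plus one extra row per shift, with no new data. The drawback is a less favourable sensitivity table.
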